## **6. Response Measures and Summary of Data Collection Methods**

### **6.1 Efficacy Measures**

[figure not shown]
#### **6.1.1 Primary Measure**

The primary efficacy measure is:

- Change from baseline in number of episodes of urinary incontinence at Week 12 as recorded by the patient in the 3-day bladder diary.

### 6.1.2 Secondary Measures

- Proportion of patients who achieve 100% reduction in urinary incontinence episodes (complete continence) from baseline (ie, baseline prior to Treatment 1)
- Change from baseline in daily average number of micturition episodes
- Change from baseline in daily average number of urgency episodes
- Change from baseline in daily average number of nocturia episodes
- Proportion of patients who have a positive treatment response on the TBS (score of either 1 or 2, representing ‘greatly improved’ or ‘improved’, respectively; see [Attachment 12.6](#) for information on completion of this questionnaire).

### 6.2 Safety Measures

- Adverse events and serious adverse events (SAEs)
- Physical examination
- Vital signs
- PVR urine volume (by bladder scan or ultrasound)
- Pregnancy test for women of childbearing potential (at screening, before study treatment[s] and at study exit)
- Urine dipstick reagent strip test
- Central laboratory urine analysis

- Urine culture and sensitivity
- Concomitant medications
- Concurrent procedures (including catheterization with associated frequency and reason for catheterization)

## **6.3 Examination Procedures, Tests, Equipment, and Techniques**

Patients who have signed an informed consent form and have met the required inclusion and exclusion criteria at the end of the screening period and at Randomization/Day 1 will be randomized and considered enrolled in the study.

Evaluations should be performed by the same evaluator throughout the study whenever possible. If it is not possible to use the same evaluator to follow the patient, then it is preferable to have the evaluations overlap (examine the patient together and discuss findings) for at least 1 visit.

### **6.3.1 Medical History**

The patient's history of OAB and other medical history (including diagnosis or symptom, date of onset, current status) and associated surgical procedures (including name of procedure and date of surgery) will be documented, as well as history of the number of UTIs occurring over the past 6 months.

### **6.3.2 Physical Examination**

The physician or appropriately qualified designee will examine the patient for any physical abnormalities of the following body systems: general appearance, HEENT (head, eyes, ears, nose, throat), heart/cardiovascular, lungs, abdomen, neurologic, extremities, back, musculoskeletal, lymphatic, skin, genitourinary (including a pelvic and rectal examination for females and rectal examination for males) and other findings.

The patient's height and weight will be recorded (height will be recorded at screening only).

### **6.3.3 Vital Signs**

Vital signs will be measured prior to any invasive procedures as outlined below.

Pulse rate (beats per minute): patients should be resting in a seated position. Pulse rate is then counted over 30 seconds and multiplied by 2.

Blood pressure (mm Hg): patients should be resting in a seated position. Systolic/diastolic blood pressure is then measured with a sphygmomanometer.

Temperature (°F or °C): patients should be seated and the body temperature taken according to local site practice.

### **6.3.4        Bladder Diary**

All patients will be provided a e-Diary in which to record electronically 3 consecutive days of required bladder diary information. Prior to receiving the e-Diary, patients will be instructed and trained on the use of the electronic diary and the data to be collected. Patients will be required to collect bladder diary data over 3 consecutive 24-hour periods during the week prior to scheduled clinic visits (for screening period only, the diary can be completed for 3 consecutive 24-hour periods at any time during the screening period). Patients must bring the e-Diary to each clinic visit. The electronic diary will capture the following information (terms used on the diary will be patient friendly):

- date and time of urinary episode
- episodes of micturition (toilet voids)
- episodes of urinary incontinence
- episodes of urgency
- episodes of nocturia (voids that awaken from normal sleep)
- start and stop date of CIC
- volume of each void measured over one 24-hour period during the 3-day bladder diary collection period. This will be used to calculate the volume voided per voiding episode (see [Section 6.3.5 Total Volume Voided](#)).

More detailed instructions on the use of the e-Diary and completion of the electronic patient bladder diary will be provided to the patient.

The electronic diary data will also be used to satisfy eligibility requirements for study entry, as well as to qualify the patient for Treatment 2.

### **6.3.5        Total Volume Voided**

The total volume of voided urine will be measured by all patients over one 24-hour period during the 3-day bladder diary collection period. Urine collection containers needed to perform this measurement will be supplied to the patients by the sites. Patients are to

measure the volume of each void (voluntary or catheterization) as it occurs and enter that amount (with time of void) into their diary.

### **6.3.6 Full Bladder Volume and Post-void Residual Urine Volume**

The investigator should assess the PVR urine volume measured at the screening visit to determine whether in his/her judgment, the patient should be using CIC to empty the bladder even if currently not doing so. In such cases, the patient should not be considered for entry into the study.

Full bladder volume (screening only) and PVR urine volume (screening and post treatment) are assessed by ultrasound or bladder scan before and after the patient has performed a voluntary void. If a patient is using CIC post treatment, the PVR urine volume will be measured after the patient has attempted to void voluntarily and prior to any catheterization (patients should not have catheterized at least 60 minutes prior to the measurement of the PVR urine volume). These procedures should be conducted at the investigational site.

After randomization, should a PVR urine volume level indicate a clinically meaningful elevation, the patient should be asked to void once again (allowing the patient sufficient time to void). The PVR urine volume will then be re-assessed. For patients who have a PVR urine volume measurement repeated, only the repeat value should be recorded in the eCRF.

Guidance on how to manage an elevated PVR urine volume, observed at any routine study visit or additional follow-up visit, is provided. In summary, post treatment PVR urine volume is divided into 3 categories:

- 1) < 200 mL
- 2) between  $\geq 200$  mL and < 350 mL
- 3)  $\geq 350$  mL

Protocol-required action depends on the PVR urine volume category, as does the need for further visits to evaluate the patient. The need for CIC is dependent on the PVR urine volume as well as the patient symptoms. This guidance is to ensure patients are appropriately followed up and CIC is only initiated when required (while also ensuring any unnecessary intervention is limited). Further details are given below.

This guidance does not preclude further actions if the investigator deems it necessary.

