## 2.2 Clinical Hypotheses

BOTOX 100 U is more effective compared to placebo, when injected into the bladder using the alternative paradigm (2 trigonal and 8 peri-trigonal injections), in reducing the number of daily urinary incontinence episodes from baseline at Week 12.

BOTOX 100 U has an acceptable/better safety profile, including the risk of incomplete bladder emptying and need for clean intermittent catheterization (CIC), when administered as 10 injections into the lower part of the bladder (2 trigonal and 8 peri-trigonal) of patients with OAB with urinary incontinence.

BOTOX 100U administered into 10 injection sites limited to the lower portion of the bladder (alternative paradigm) rather than 20 sites in the posterior wall is effective in achieving efficacy in patients with OAB while reducing the risk of incomplete bladder emptying in those patients.

BOTOX 100 U, administered using an alternative injection paradigm, is effective for longer duration than placebo as assessed by the difference between treatment groups in the time to qualification for second treatment (qualification for Treatment 2 criteria provided in [Section 5.10.1](#) Request/Qualification for Treatment 2) during the 30 weeks of follow-up after the first treatment injection.

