## **10.4 Documentation**

### **10.4.1 Source Documents**

Source documents may include a patient's medical records, hospital charts, clinic charts, the investigator's patient study files, as well as the results of diagnostic tests such as x-rays, laboratory tests, scans and ultrasound reports. The investigator's copy of the eCRF serves as part of the investigator's record of a patient's study-related data.

The following information should be entered into the patient's medical record:

- patient's name
- patient's contact information

- date that the patient entered the study and medication kit number
- study title and/or the protocol number of the study and the name of Allergan
- a statement that informed consent was obtained (including the date). A statement that written authorization (US sites only) or other country and local patient privacy required documentation for this study has been obtained (including the date)
- dates of all patient visits
- medical and surgical history
- previous anticholinergic use and reason for discontinuation
- all concurrent medications. (List all prescription and non-prescription medications being taken at the time of enrollment. At each subsequent visit, changes to the list of medications should be recorded).
- dates of study treatment administration
- date(s) of patient request for retreatment and reason
- date of qualification for retreatment
- occurrence and status of any adverse events (including any procedure-related adverse events)
- post-void residual urine volumes
- physical examination findings, including height and weight
- vital signs
- date the patient exited the study, and a notation as to whether the patient completed the study or reason for discontinuation
- results of laboratory tests performed by the site (eg, results of urine pregnancy tests, urine dipstick)
- results, if applicable, of any procedures performed to confirm eligibility criteria (eg, follow-up on abnormal urine cytology findings, etc.)
- reason, if applicable, de novo CIC not discontinued in accordance with criteria stated in [Section 6.3.6.2 Post-void Residual Urine Volume  \$\geq\$  200 mL and < 350 mL](#)

Patient's response to the following questionnaire/assessments entered directly onto the appropriate electronic form will be considered source data:

- I-QOL questionnaire
- TBS questionnaire
- Patient bladder diary

In addition, study drug accountability and reconstitution records will be retained as source documentation.

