5.5.4 Analysis of Time to Request of Re-Treatment

The time-to-request of re-treatment between the two treatments will be analyzed using the log-rank test. Kaplan-Meier estimates of the time-to-request of re-treatment will be provided. A 95% CI for the median time-to-request of re-treatment for each treatment will be calculated.

6 Safety Analyses

All safety analyses will be conducted on the safety population. No inferential comparison between treatment groups will be performed for the safety analysis.

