6.9 Post-void residual (PVR) urine volume

PVR urine volume will be summarized descriptively for each treatment by visit. Change from baseline in PVR urine volume will be summarized.

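### Only the repeat of an elevated post-treatment PVR enters the eCRF, so the PVR summaries mix single-void and second-void values without a flag and are biased downward

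*Protocol*

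**What the plan says.** Protocol 6.3.6 sets the trigger: "After randomization, should a PVR urine volume level indicate a clinically meaningful elevation, the patient should be asked to void once again". The PVR is then measured again, and the recording rule follows: "For patients who have a PVR urine volume measurement repeated, only the repeat value should be recorded in the eCRF". That sentence gives no volume in mL for the trigger. The 200 and 350 mL categories that follow in the same section govern clinical action and are not stated as the trigger for the repeat.

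PVR is a listed safety measure (Protocol 6.2). Protocol 7.3.4 plans a summary by visit and a change from baseline. SAP 6.9 repeats this: "PVR urine volume will be summarized descriptively for each treatment by visit", with change from baseline also summarized. The SAP text available has no rule on first versus repeat readings.

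Emptying is part of the trial's rationale. One hypothesis in Protocol 2.2 is that the 10-site pattern is effective "while reducing the risk of incomplete bladder emptying in those patients". Section 6 of the SAP opens by limiting safety to description: "No inferential comparison between treatment groups will be performed for the safety analysis".

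Two other places matter. The exclusion criteria in the Protocol Summary allow the screening PVR to be repeated once. Protocol 10.4.1 lists "post-void residual urine volumes" among the entries for the patient's medical record, without saying whether a first reading that was later repeated is included.

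**The concern.** The rule acts in one direction. Only readings that look high are repeated, and the repeat follows an extra void. Two things then lower the recorded value: regression to the mean, because the first reading was selected for being high, and the additional emptying. No matching step raises a low reading.

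The by-visit tables would hold single-void residuals for most patients and second-void residuals for those who looked worst, and nothing in the data would tell them apart. Because the trigger is left to judgment, sites may also differ in whose first reading is replaced.

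The procedure is the same in both blinded arms, but its effect is not equal. An arm with few elevations has little to lose, so the shift falls mainly on the arm with more of them and narrows the described difference. With safety analysed descriptively, these tables are the planned quantitative evidence on residual volume.

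**Working it through.** The plan gives no figure for the effect of this rule, so there is none to reproduce. The sample size (102 evaluable, 114 randomized) rests on incontinence episodes alone; PVR does not enter it. Everything below is illustration on assumed inputs.

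**1. Patient counts.** Inputs: BOTOX arm N = 114 × 2/3 = 76. Share with a first reading of at least 200 mL, p = 9%, borrowed as an upper illustration from Protocol Section 1. That figure (less than 9%) is for a change from baseline of at least 200 mL at any time in Phase III, so it is only a stand-in. The share f of such readings that fall below 200 mL on repeat is not in the documents; assumed 0 to 75%.

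Expected recorded count = N × p × (1 − f):
- f = 0: 76 × 0.09 = 6.8 patients (9.0%)
- f = 25%: 6.84 × 0.75 = 5.1 (6.8%)
- f = 50%: 6.84 × 0.50 = 3.4 (4.5%)
- f = 75%: 6.84 × 0.25 = 1.7 (2.3%)

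**2. Second void only, no measurement error.** Assume PVR is lognormal with median m and log-SD s, the repeat is triggered at 200 mL, and the second void leaves a fraction k of the residual. A first reading below 200 mL stays below, so for a cut c of 200 mL or more:

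P(recorded ≥ c) = 1 − Φ( ln(c / (k·m)) / s )

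For a higher-PVR arm, m = 50 mL and s = 1.0:

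| k | ≥ 200 mL | ≥ 350 mL |
|---|---|---|
| 1 (first readings) | 8.3% | 2.6% |
| 0.90 | 6.8% | 2.0% |
| 0.75 | 4.7% | 1.3% |
| 0.50 | 1.9% | 0.4% |

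For a low-PVR arm, m = 22 mL and s = 0.75, the first-reading share at or above 200 mL is 1 − Φ(ln(200/22)/0.75) = 1 − Φ(2.94), about 0.16%. At k = 0.75 it is about 0.04%. The between-arm difference goes from 8.3 − 0.16 = 8.1 points to 4.7 − 0.04 = 4.7 points. Nearly all of the shrinkage comes from the higher-PVR arm.

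**3. Measurement error added.** Simulation over median 40 to 60 mL, log-SD 0.9 to 1.0, measurement CV 15% to 25%, second void removing 0 or 30%, repeat triggered at 200 mL. Recorded value = repeat if the first reading is at least 200 mL, otherwise the first reading.
- No extra emptying: net loss from the ≥ 200 mL category 14% to 31%; from ≥ 350 mL 0 to about 4%; mean lower by 0.4 to 2.5 mL.
- Second void removes 30%: the loss reaches about 63% at ≥ 200 mL and about 68% at ≥ 350 mL; mean lower by about 4 to 15 mL.
- The median is essentially unchanged throughout, because readings near 40 to 60 mL are never repeated.

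Regression to the mean therefore explains part of the loss at 200 mL and almost none at 350 mL. The rest is the assumed extra emptying.

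**The case against.** The strongest points on the other side are these.

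- A residual measured after a full opportunity to void is a defensible measure of incomplete emptying, and the protocol wants to limit unnecessary intervention. Preferring the first reading would be a choice, not a correction. This stands, and is why both readings should be shown.
- A reader might infer that elevated residual volumes are removed from the safety data. The documents do not support that. A reading still raised after the second void is recorded and falls under the 200 and 350 mL categories, the extra visits, catheterization and the retention adverse event (Protocol 6.3.6 to 6.3.7, 9.1.2). An investigator may also record a residual-volume event, and catheterization use is summarized separately. None of these routes restores the unrecorded first reading to the PVR tables. The residual-volume event is also discretionary and does not say which reading counts.
- A reader might infer that the rule flatters the 10-site pattern against the 20-site one. There is no 20-site arm, and the documents do not say how repeats were recorded in Phase III, so the effect on that outside comparison is unknown. If Phase III used the same rule, first readings alone would spoil the comparison.
- The visible SAP plans means, SDs, medians and extremes for PVR, not counts above a cut. The percentage losses therefore describe a tabulation that may not be planned; the shift in the mean describes one that is. The mean, SD and maximum are affected and the median hardly at all.
- Using first readings after treatment against a baseline that was itself a repeat would inflate change from baseline. This stands and shapes the remedy.

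**Conclusion.** The concern holds in a limited form. First elevated readings, including all elevations that resolve on re-voiding, are absent from the planned PVR summaries. Those summaries mix two kinds of measurement without a flag and are biased downward, more in the arm with more elevations.

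The direction follows from the rule. The size does not follow from anything in the documents: the distribution, measurement error, second-void effect and 200 mL trigger are all assumed. On those assumptions, roughly 14% to 63% of readings at or above 200 mL leave that category and the mean falls by about 0.4 to 15 mL. If every repeat stays at or above 200 mL, no patient leaves that category.

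This is a loss of safety data that is cheap to prevent. It does not touch the primary efficacy analysis.

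**What to change.** 1. Change the recording sentence in Protocol 6.3.6 so that both the first and the repeat PVR go into the eCRF, with a repeat flag. Apply this at screening too, so that baseline is handled the same way.
2. In SAP 6.9, present PVR by visit and change from baseline on both the first-reading and the repeat-reading basis. Within each, use the same basis at baseline and after treatment; where no repeat was made, the single reading serves both.
3. State which reading the existing PVR category, catheterization and adverse event passages refer to, leaving those clinical rules as they are. Without this, a stored first value of 350 mL or more with a lower repeat and no catheterization could look like a deviation from Protocol 6.3.6.3.

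The cost is one extra eCRF field with its flag, one extra table column and a clarifying sentence. Both values are already measured, and sample size is unaffected.

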### **6.3.6.1 Post-void Residual Urine Volume < 200 mL**

No protocol-required action needs to be taken. The patient continues to be reviewed as per the schedule of visits and procedures. CIC may be initiated only if the investigator deems it necessary for patient safety and will be recorded as a clinical decision.

### **6.3.6.2 Post-void Residual Urine Volume $\geq$ 200 mL and $<$ 350 mL**

If a PVR urine volume of  $\geq$  200 mL but  $<$  350 mL is identified at any post treatment visit, the investigator will assess the patient for any spontaneously reported associated symptoms (such as voiding difficulties or sensation of bladder fullness), with the resulting action to be as follows:

- 1) if a patient reports associated symptoms that in the opinion of the investigator require CIC to be initiated, then CIC should be managed as detailed in the CIC section.
- 2) if a patient does not report any symptoms or if they report associated symptoms that, in the opinion of the investigator, do not require CIC then the following will occur:
  - a. the patient will be seen for an additional follow-up visit 1 week later, at which time the PVR urine volume and any associated symptoms will be reassessed and central laboratory urine analysis and culture/sensitivity will be performed. At this reassessment visit:
    - i. if the PVR urine volume is increasing and is associated with symptoms, that in the investigator's opinion require CIC, then CIC should be initiated and managed as detailed below in the CIC section
    - ii. if the PVR urine volume is  $\geq$  350 mL then CIC should be initiated and managed as detailed below in the CIC section
    - iii. if the PVR urine volume is increasing but is not associated with symptoms or is associated with symptoms that in the opinion of the investigator do not require CIC, then the patient will be seen 1 week later to determine if CIC has become warranted and should be initiated based on PVR urine volume and/or any associated symptoms. At this additional reassessment visit:
      1. a central laboratory urinalysis and culture/sensitivity will be collected

2. if in the investigator's judgment CIC should be initiated, then CIC should be managed as detailed below in the CIC section
3. if CIC is not initiated and PVR urine volume continues to increase, the investigator will determine whether additional follow-up visits should occur
- iv. if the PVR urine volume is decreasing or is unchanged then the patient will continue per the protocol schedule of visits and procedures.

### **6.3.6.3 Post-void Residual Urine Volume $\geq 350$ mL**

If a PVR urine volume of  $\geq 350$  mL is identified at any post treatment visit (regardless of symptoms) then CIC will be initiated as detailed in the CIC section.

### **6.3.7 Clean Intermittent Catheterization**

The following guidance should be used for the initiation of CIC in this study. Sterile, single-use intermittent catheters should be used. Indwelling catheters should not be used in this study; therefore, the Allergan Medical Safety Physician should be informed if an indwelling catheter is needed.

#### **6.3.7.1 Initiation of Clean Intermittent Catheterization**

As described above in the PVR urine volume section, CIC should be initiated per protocol when one of the following criteria is fulfilled:

- PVR urine volume is  $\geq 350$  mL at any post treatment visit, regardless of whether the patient reports associated symptoms
- PVR urine volume is  $\geq 200$  mL and  $< 350$  mL and the patient spontaneously reports associated symptoms (ie, voiding difficulties, sensation of bladder fullness) that in the opinion of the investigator require CIC

The following will occur when initiating CIC (for elevated PVR urine volume as described above):

- 1) CIC is implemented and the patient should be instructed to perform CIC using sterile, single-use catheters (which will be provided to the patient)
- 2) an adverse event of urinary retention is recorded
- 3) central laboratory urine analysis and culture/sensitivity are performed as per routine requirements at each study visit excluding the clinic visit at Week 24.

- 4) the patient will be seen for a follow-up visit 1 week later where the PVR urine volume, associated symptoms, central laboratory urine analysis and culture/sensitivity will be reassessed. The investigator will determine whether the patient can then be followed per protocol scheduled study visits or whether additional follow-up visits should occur.

Once CIC is initiated, the status of CIC use should be documented in the patient record at each visit (ie, use/non-use). Start date of CIC should be documented, also.

